## 9 STATISTICAL METHODS

### 9.1 Subject Disposition

The number of subjects randomized and the number and percentage of subjects in the safety population, completed and discontinued, and entered each study period will be summarized for all randomized subjects by age group (4-11 years, 12-17 years, 4-17 years) and treatment group (AR101, placebo, and total).

Reasons for discontinuation from the study will be summarized. In addition, subjects who require follow-up due to chronic/recurrent GI adverse events will be summarized.

Subject completion status, date of study completion/discontinuation, study treatment discontinuation, and reason for discontinuation will be listed based on the information collected on the case report form.

Inclusion and exclusion eligibility will be listed separately.

### 9.2 Protocol Deviations

A protocol violation (ie, major protocol deviation) is a deviation from the protocol approved by the institutional review board or ethics committee that may affect the subject's rights, safety, or well-being and/or the completeness, accuracy, and reliability of the study data. In addition, protocol violations include willful or knowing breaches of human subject protection regulations or policies; any action that is inconsistent with medical and ethical principles; and a serious or continuing noncompliance with federal, state, local, or institutional human subject protection regulations, policies, or procedures.

A nonmajor protocol deviation is any change, divergence, or departure from the study design or procedures that does not have a major impact on the subject's rights, safety, or well-being or the completeness, accuracy, and reliability of the study data.

All protocol deviations will be reported in the data system on a specific case report form according to the following categories:

- Inclusion criteria
- Exclusion criteria
- Received incorrect study treatment
- Randomization issue/ randomized to wrong stratum
- Informed consent form
- Serious adverse event not reported
- Visit out of window
- Missed study visit
- Procedure not per protocol

- Prohibited concomitant medication
- Laboratory sample missed
- Study Product compliance
- Other (with free text field to record details)

Protocol deviations will be reviewed and their categorization as major or minor will be determined before database lock. Major protocol deviations will be summarized for the safety population by age group (4-11 years, 12-17 years, 4-17 years) and treatment group (AR101, placebo, and total). All protocol deviations, both major and nonmajor, will be listed for all randomized subjects.

### **9.3 Demographics and Baseline Characteristics**

Demographic and baseline characteristics will be listed for all randomized subjects.

Summary statistics for demographics and baseline characteristics will be summarized for the safety population by age group (4-11 years, 12-17 years, 4-17 years) and treatment group (AR101, placebo, and total). Demographic data will include age, race, ethnicity, sex, body weight, height and body mass index (BMI). Baseline characteristics include total IgE, peanut-specific (ps)-IgE, ps-IgG4, ps-IgE/IgG4 ratio, results from SPT, childbearing potential, and history of asthma.

Age will be calculated relative to date of informed consent for ARC007, as follows:

- If the month and day portion of the informed consent date is prior to the month and day portion of the birthdate, age will be calculated as the year of informed consent minus the year of birth, minus 1;
- If the month and day portion of the informed consent date is on or after the month and day portion of the birthdate, age will be calculated as the year of informed consent minus the year of birth.

### **9.4 Disease Characteristics and Previous Therapies**

#### **9.4.1 Peanut Allergy History**

Peanut allergy history will be listed for all randomized subjects.

The duration of peanut allergy (months since peanut allergy diagnosis), months since qualifying allergic reaction to peanut, medication given for qualifying allergic reaction to peanut, number of anaphylactic reactions to peanut in lifetime, months since most recent reaction to peanut, and the allergy symptoms experienced during the most recent peanut exposure will be summarized for the safety population by age group (4-11 years, 12-17 years, 4-17 years) and treatment group (AR101, placebo, and total).

The reported date of the reaction and date of diagnosis of peanut allergy will be imputed based on the logic in [Section 7.2.1](#).

#### 9.4.2 Nonpeanut Allergy History

All nonpeanut allergy history will be listed for all randomized subjects. The presence of nonpeanut allergy history and type of allergy will also be summarized for the safety population by age group (4-11 years, 12-17 years, 4-17 years) and treatment group (AR101, placebo, and total).

#### 9.4.3 Other Medical History

Medical history will be listed by subject and body system for all randomized subjects. Subjects with abnormal medical history events will be summarized for the safety population by age group (4-11 years, 12-17 years, 4-17 years), treatment group (AR101, placebo, and total) and by the Medical Dictionary for Regulatory Activities (MedDRA) system organ class (SOC) version 19.1 and preferred term.

### 9.5 Extent of Exposure and Compliance

Study treatment exposure will be summarized for the safety population by age group (4-11 years, 12-17 years, 4-17 years), treatment group (AR101, placebo) and study period (initial escalation, up-dosing, 300 mg QD, and overall).

First and last dose dates for each study period will be identified as follows:

Study Period	First Dose Date	Last Dose Date
Initial escalation	Date of first dose at the study site on initial escalation day 1	Date of last dose at initial escalation day 1 or day 2 at the study site
Up-dosing	The day following the date study product was dispensed at initial escalation day 2	Date of first dose of 300 mg at the end of the up-dosing 300 mg visit if dose is tolerated and subject continues to at-home 300 mg QD dosing. If first in-clinic 300 mg dose is not tolerated and dose is immediately reduced, the last dose date of up-dosing will be when the first in-clinic 300 mg dose is tolerated and subject continues to at-home 300 mg QD dosing. For subjects who do not reach the 300 mg dose, the latest of the last dose during up-dosing at the study site and the last dose at home
300 mg QD	Date of first dose of study product of 300 mg at home. This is defined as the day following the first in-clinic visit where the 300 mg dose was tolerated and 300 mg study product was first dispensed.	Date of last dose of study product for subjects who enter 300 mg QD study period
Overall	Date of first dose at the study site on initial escalation day 1	Last dose of study product prior to exit visit in ARC007

The total amount of study product consumed will be calculated as the sum of doses at the study site plus the sum of doses taken at home as recorded in the dosing diary.

The following calculations of study product exposure will be made and summarized:

- Duration of exposure (in days and in months): calculated as the date of the last dose of study product minus the date of the first dose of study product plus 1 during the study period, except for initial escalation, the duration of exposure will only be 1 or 2 days depending on whether study product was taken on initial escalation day 1 and initial escalation day 2. Duration of exposure will be summarized using descriptive statistics for continuous endpoints and categorically by 28-day increments for the overall treatment period:  $\leq 28$  days, 29–56 days, ... 337–364 days, and  $> 364$  days.
- Total dose consumed (mg): calculated as the cumulative sum of all doses taken during the study period.
- Average dose per day (mg): calculated as the total dose consumed divided by the number of days during the study period.
- Number of unsuccessful dose increases: where an unsuccessful dose increase is defined as a single dose at the study site at a higher dose level followed by an immediate return to the previous dose level or a lower dose level.
- Number of dose reductions: where a dose reduction is defined as any decrease in dose level that does not qualify as an unsuccessful dose increase.
- Maximum dose achieved (mg/day): summarized using descriptive statistics for continuous endpoints and categorically using all possible dose levels: 0.5, 1, 1.5, 3, 6, 12, 20, 40, 80, 120, 160, 200, 240, or 300 mg/day.
- Time to 300 mg dosing and time to 80 mg dosing for the overall treatment period using Kaplan-Meier methodology. Time will be calculated as date of the first 300 mg (or 80 mg) dose minus the first dose date +1. Subjects who do not reach the specified dose will be censored at the date of their last study product dose.

The nonmissing valid diary entries will be used to estimate dosing compliance at home. The following measures of compliance with dosing at home will be calculated:

- Total number of planned dosing days at home: calculated as the number of days where a valid diary entry was made, but excluding entries where a dose was missed because of investigator orders.
- Percentage of planned dosing days where a full or partial dose was consumed.
- Percentage of planned dosing days where a full dose was consumed.
- Percentage of planned dosing days where a partial dose was consumed.
- Percentage of planned dosing days where a dose was missed.

Data for dosing at home will be listed. Daily diary records, including date and time, whether a full or partial dose was consumed (or the dose was missed), and the reason for partial or missed doses will be listed. If any dose-related allergy symptoms are present, the symptoms and medications to treat the symptoms will also be listed.

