3.2 Initial Escalation

All Initial Escalation doses will be administered by investigational site personnel to the subjects under direct supervision. Eligible subjects will be randomized and receive treatment with IP on Day 1, starting at a dose of 0.5 mg, increasing the dose at 20- to 30-minute intervals to a maximum dose of 6 mg ([Table 1](#)), according to the Schedule of Events (SOE) in [Appendix 1](#). Subjects who fail to tolerate ≥ 3 mg dose on Day 1 will be considered escalation failures and will be discontinued. Subjects who tolerate ≥ 3 mg dose on Day 1 will undergo confirmatory dosing of a single 3 mg dose on the following day, Day 2. Subjects who do not tolerate this confirmatory dose will be discontinued. Subjects who tolerate this confirmatory dose will enter the Up-Dosing Period.

Table 1: Initial Escalation Schedule

Initial Escalation Schedule		
Day 1 Dose Number	Investigational Product Dose, mg ^a	Cumulative Dose, mg
1	0.5	0.5
2	1	1.5
3	1.5	3
4	3	6
5	6	12
Day 2 Dose Number	Investigational Product Dose, mg	Cumulative Dose, mg
1	3	3

^a All mg doses shown refer to milligrams of peanut protein or the equivalent placebo dose.

Doses will be delivered at 20 to 30 minute intervals under direct observation.

Capsules are to be opened, contents sprinkled over an age-appropriate food, and mixed thoroughly and consumed.

Day 1: Subjects who are unable to tolerate at least a single dose of 3 mg at the end of Day 1 will be considered escalation failures. Subjects who tolerate ≥ 3 mg on Day 1 will return on Day 2 to receive a 3 mg single dose.

Day 2: Subjects with either no symptoms or mild symptoms on Day 2 at 3 mg will start daily home-dosing at 3 mg on Day 3.

Subjects with moderate or severe symptoms at 3 mg on either Day 1 or Day 2 will be considered escalation failures and will be discontinued from the study.

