#### **9.8.6 Allergy Symptoms During Dosing at the Study Site**

During study product dosing at the study site, the severity of prespecified allergy symptoms is rated as mild, moderate, severe, life-threatening, or death. In addition, the presence of dose-limiting allergy symptoms is recorded for each dose.

The number of subjects experiencing any dose-related allergy symptoms during study product dosing at the study site and the maximum severity of symptoms will be summarized at each dose level. If a subject is administered the same dose at more than 1 study site visit (eg, dose was the same as the previous visit or dose was increased with a subsequent dose reduction), the most severe symptoms will be summarized for that dose level.

The time from dose administration to the time of onset of the first allergy symptom will be summarized using descriptive statistics and presented by dose level. Time from onset of the first symptom to resolution of the last symptom will be summarized similarly. If a subject receives more than 1 dose of study product at the study site at the same dose level, the subject will be counted only once using the shortest time from dose administration to onset of

the first symptom and the longest time from onset of first symptom to resolution of last symptom.

All summaries will be presented for the safety population by age group (4-11 years, 12-17 years, 4-17 years), and treatment group (AR101, placebo).

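### SAP 9.5 counts the scheduled step from 6 mg (Day 1) to 3 mg (Day 2) as an unsuccessful dose increase, which inflates the initial-escalation and overall counts in both arms

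*SAP*

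**What the plan says.** **Schedule.** Protocol 3.2 and Table 1 give Day 1 site doses of 0.5, 1, 1.5, 3 and 6 mg, "increasing the dose at 20- to 30-minute intervals to a maximum dose of 6 mg". Children who tolerate at least 3 mg on Day 1 "will undergo confirmatory dosing of a single 3 mg dose on the following day, Day 2". Protocol 6.3.1 sends two groups to that Day 2 visit: children with no dose-limiting symptoms on Day 1, and children whose dose-limiting symptoms occurred only at 6 mg.

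**Counting rules.** In SAP 9.5, "an unsuccessful dose increase is defined as a single dose at the study site at a higher dose level followed by an immediate return"; going back to the earlier level, or to any lower one, qualifies. A dose reduction is the residual category: "any decrease in dose level that does not qualify as an unsuccessful dose increase". Exposure is summarised by age group, treatment group and "study period (initial escalation, up-dosing, 300 mg QD, and overall").

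**Maximum dose.** The same section specifies "Maximum dose achieved (mg/day): summarized using descriptive statistics for continuous endpoints and categorically using all possible dose levels". The list of levels includes 0.5, 1 and 1.5 mg, which are given only on Day 1.

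**The concern.** The drop from 6 mg to 3 mg is part of the design, yet it meets every element of the SAP definition: one site dose, at a higher level, followed at the next dose by the level before it. A genuine failed increase during up-dosing looks the same in the dosing data, because under Protocol 6.5.5.1 the child returns the next day for the last tolerated dose. A program that follows the wording cannot separate the two.

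Tolerability is part of the primary objective, and these counts describe how the escalation schedule was tolerated. In the initial-escalation column the count mostly marks children who completed the schedule, under a label that says the opposite. The overall column carries the same added count. The maximum-dose summary has a related but narrower problem: a single 6 mg dose on Day 1 can be shown as 6 mg/day.

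**Working it through.** **1. Reproduce the plan's figure.** The cumulative Day 1 dose in Table 1 is 0.5 + 1 + 1.5 + 3 + 6 = 12 mg, as stated. The documents give no expected number of unsuccessful increases to reproduce.

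**2. Apply the SAP 9.5 rule literally.** At each drop in dose, ask whether the higher dose was a single site dose above the one before it, and whether the next dose was at or below that earlier level. If yes, it is an unsuccessful increase; otherwise it is a dose reduction. On Days 1 and 2 the sequence is 0.5, 1, 1.5, 3, **6, 3**. The 6 mg dose exceeds the preceding 3 mg and the next dose is 3 mg, so it counts as an unsuccessful increase. Both doses fall in initial escalation, because the SAP 9.5 period table starts up-dosing on the day after Day 2 dispensing.

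| Course | Initial escalation | Up-dosing | Overall | Overall maximum |
|---|---|---|---|---|
| Whole schedule tolerated to 300 mg | 1 | 0 | 1 | 300 |
| Day 1 ended at 3 mg, then perfect to 300 mg | 0 | 0 | 0 | 300 |
| Whole schedule, one real failed step at 80 mg | 1 | 1 | 2 | 300 |
| 6 mg on Day 1, stopped during 3 mg/day | 1 | 0 | 1 | 6 |
| 6 mg on Day 1, stopped at 12 mg/day | 1 | 0 | 1 | 12 |
| Dose-limiting symptoms at or before 3 mg on Day 1 | 0 | none | 0 | at most 3 |

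The 300 mg QD count is 0 wherever that period is entered, and dose reductions are 0 in every row. Severe symptoms at 6 mg on Day 1 lead to discontinuation under Protocol 6.5.4, so that child also scores 0.

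**3. Number of children.** The share who take 6 mg on Day 1 and are dosed on Day 2 is not in the documents. For an assumed share s of 500 children, the number affected is 500 × s:

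- s = 0.50: 250
- s = 0.80: 400
- s = 0.95: 475
- s = 1.00: 500

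These totals include children with dose-limiting symptoms only at 6 mg, for whom the count is correct.

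**4. Effect on the overall mean.** Assume, for illustration only, mean counts apart from this step of 0.5 (AR101) and 0.1 (placebo): a difference of 0.4 and a ratio of 5.0.

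- All children affected: 0.5 + 1 = 1.5 and 0.1 + 1 = 1.1. The difference stays at 0.4; the ratio is 1.5 / 1.1 = 1.36.
- Shares of 80% (AR101) and 95% (placebo): 0.5 + 0.80 = 1.30 and 0.1 + 0.95 = 1.05. The difference becomes 0.25 and the ratio 1.24.

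**5. Check the repair.** With the step excluded from both counts, the perfect course goes from 1 to 0 and the course with a failure at 80 mg from 2 to 1; reductions stay at 0. With the step excluded from the unsuccessful-increase count alone, the residual definition catches it, and the perfect course shows 1 dose reduction instead of 0.

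**The case against.** The best defence is that the count was meant for up-dosing only. The SAP does not say so, and its text points the other way. The section summarises initial escalation as a period, lists levels that occur only on Day 1, and writes an explicit exception for initial escalation under duration of exposure but none here. The tables are programmed by a separate organisation (SAP 1), so the wording matters.

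A second defence is that little depends on the count. That largely stands. It is descriptive, no between-group test is planned, the up-dosing column is clean, and tolerability is also described by discontinuations due to adverse events and by Kaplan-Meier time to 80 mg and 300 mg.

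Some stronger readings are tempting but not supported:

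- **That children are misclassified as escalation failures.** Protocol 3.2 and 3.3 define that status by tolerability in initial escalation and by reaching 300 mg within 40 weeks. The SAP does not derive it from this count.
- **That nearly every child receives a false count.** The share is not documented, and children with dose-limiting symptoms only at 6 mg are true counts.
- **That the treatment difference is hidden.** With equal shares affected, the absolute difference survives, and the up-dosing column shows it undistorted.
- **That SAP 9.8.6 makes the same error by pooling the two 6 mg occasions.** For a dose level repeated at another site visit, it states that "the most severe symptoms will be summarized for that dose level". That is a prespecified worst-case choice; wanting a split by period is a preference.

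On maximum dose, including Day 1 levels looks deliberate. What remains is the mg/day label and its effect on one small group.

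**Conclusion.** The point holds as a derivation error of limited reach. Read literally, SAP 9.5 adds exactly one unsuccessful increase, in the initial-escalation and overall summaries, for each child in either arm who takes 6 mg on Day 1 and is dosed on Day 2. That is 250 to 500 children if the share is 50% to 100% of the full 500; the range is an assumption. Within initial escalation the measure is close to inverted: children stopped at or before 3 mg score 0, while those who complete the schedule score 1. The count also does not distinguish a child who tolerated 6 mg from one who did not.

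The overall ratio between arms is compressed. The overall absolute difference is distorted only if the arms differ in the share affected. The maximum-dose issue alters the overall column only for children who took 6 mg on Day 1 and never went beyond 3 mg/day; in the initial-escalation column it is a matter of units.

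**What to change.** In SAP 9.5:

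1. Start both the unsuccessful-increase and dose-reduction counts at up-dosing, or state that the scheduled Day 1 to Day 2 step is excluded from both.
2. For initial escalation, report the number of children with dose-limiting symptoms at each Day 1 dose. SAP 9.8.6 confirms that this is recorded for every site dose.
3. Report the highest Day 1 single dose in mg separately from the maximum daily dose in mg/day, so that a child who stopped during 3 mg/day is not shown as having achieved 6 mg/day.

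The cost is a few sentences of SAP text and minor programming, with no new data and no change to conduct.

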7.9.2 Individual Stopping Rules

Individuals may stop the study at any time by withdrawing their consent if they experience subjectively intolerable AEs, dosing symptoms, or for any other reason. In addition, > 7 consecutive days of missed daily dosing due to non-compliance (ie, for any reason other than treatment of an AE or an IP dispensing error) constitutes an individual stopping rule. During Up-dosing, subjects must halt up-dosing and re-start with a reduced dose if more than 4 days of dosing are missed. Missing 3 or more consecutive days on 3 occasions is an individual stopping rule, as is missing 15 or more consecutive days of dosing for any reason, with one exception of the voluntary 4-week hiatus for GI AEIs occurring at or before the 20 mg dose, as specified in Section 6.5.3.2.

Occurrence of any of the following will result in the cessation of dosing and the subject being discontinued from the study as an escalation failure non-responder, resulting in an Early Discontinuation Visit within 14 days:

- Failure to accomplish up-dosing of IP after 3 attempts
- Failure to identify a tolerated dose of IP after 3 attempts at dose reduction

Finally, administration of 3 or more doses of epinephrine for the treatment of any dose-related allergic reaction in any subject is an individual stopping rule.

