## 7 DEFINITIONS, DERIVATIONS, AND CONVENTIONS

### 7.1 Definitions and Derivations

- Study day is calculated as (assessment date – first dose date + 1) for assessments and visits performed on or after the first dose date, and (assessment date – first dose date) for assessments and visits prior to the first dose date.
- Baseline is defined as the last nonmissing value prior to the first dose of randomized study treatment in ARC007.
- Change from baseline is calculated as the observed value after the first dose – baseline value.
- The screening period is defined as the time beginning with the date and time of informed consent through the day prior to randomization.
- Initial escalation is defined as the time beginning with the date and time of the first dose of randomized study product at the study site and ending with the date of the last dose of randomized study product taken prior to up-dosing.
- Up-dosing is defined as the time beginning with the date and time of the first dose of study product at 3 mg at home, and ending with the date and time of first dose at

300 mg at the study site. Up-dosing will be approximately 20 weeks in duration, but may be extended to a maximum of 40 weeks to accommodate dose reductions and re-escalations, if necessary.

- A 300 mg QD period will be defined as the time beginning with the date and time of the first dose of study product at 300 mg at home and ending with the date of the last dose of study product. This period will be ideally approximately 2 weeks in duration at the end of ARC007, but dosing may continue up to a maximum of 48 weeks after day 1 to ensure tolerability of 300 mg prior to exiting ARC007. Some subjects continued to receive 300 mg doses in ARC007 after the expected rollover date while waiting for activation of ARC008 or ARC011 at the study site. The 300 mg doses as a result of the rollover delay will be included in the 300 mg QD period.

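### SAP 9.5 dates time to 300 mg and 80 mg from the first dose given, tolerated or not, while its own 300 mg period rules require a tolerated dose, and SAP 7.1 does not match them

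*SAP*

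**What the plan says.** SAP 9.5 lists time to 300 mg and time to 80 mg among the exposure calculations. The event date is fixed by "Time will be calculated as date of the first 300 mg (or 80 mg) dose minus the first dose date +1", and the censoring rule is "Subjects who do not reach the specified dose will be censored at the date of their last study product dose". The word *reach* is not defined.

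The period table in the same section applies a stricter rule at 300 mg. For the end of up-dosing it says "If first in-clinic 300 mg dose is not tolerated and dose is immediately reduced, the last dose date of up-dosing will be when" a first in-clinic 300 mg dose is tolerated and the child goes on to 300 mg at home. For the start of the 300 mg QD period it says "This is defined as the day following the first in-clinic visit where the 300 mg dose was tolerated" and home supply was first dispensed. SAP 9.8.1 allocates adverse events to periods by the same tolerated-dose rule, with the stated aim of leaving no gap between periods.

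SAP 7.1 differs. It describes up-dosing as starting with the first 3 mg home dose "and ending with the date and time of first dose at" 300 mg at the study site, with no tolerance condition. It starts the 300 mg QD period at the first 300 mg dose at home.

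For the highest dose, SAP 9.5 gives only the display: "Maximum dose achieved (mg/day): summarized using descriptive statistics for continuous endpoints and categorically using all possible dose levels", from 0.5 to 300 mg/day. It does not say whether *achieved* means given or tolerated.

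**The concern.** One section uses two meanings of reaching 300 mg. Take a child who is given 300 mg in clinic, does not tolerate it, steps down, and never tolerates it later. The period table's tolerated-dose rule never yields a date for this child, so the only clause left is the one for children who do not reach 300 mg. The time-to-dose formula gives the same child an event date. Two programmers could therefore treat this child differently, one as an event and one as censored. Under Protocol 6.3.3 and 7.9.2 ("Failure to accomplish up-dosing of IP after 3 attempts") the child is an escalation failure if the attempts are repeated without success.

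The direction of any error is fixed: the first dose given can never be later than the first dose tolerated. These curves describe how fast children reach the target dose in a trial whose primary objective is safety and tolerability.

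The mismatch with SAP 7.1 reaches beyond the exposure tables. Days in the up-dosing period are the denominator for exposure-adjusted event rates (SAP 9.8.1). They also bear on the secondary endpoint of allergic reactions during up-dosing normalized for treatment duration (SAP 4.2). Under 7.1, the weeks between a failed first 300 mg site dose and the first 300 mg home dose belong to neither period.

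**Working it through.** The plan gives no figure on this point to reproduce. The check applies the SAP's date formula to the protocol's schedule.

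**Inputs.** Protocol Table 2 has ten 2-week intervals before 300 mg and five before 80 mg. Protocol 6.5.5.1 keeps a child on the reduced dose for about 2 more weeks after a first dose with moderate symptoms. Protocol 6.3.3 makes three consecutive failed escalation attempts an escalation failure. Protocol 9.4 gives up to 500 children randomized 2:1.

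**Schedule.**
- First 300 mg visit: 10 × 2 = 20 weeks, which agrees with the 20-week minimum in Protocol 6.3.3.
- First 80 mg visit: 5 × 2 = 10 weeks, which agrees with the approximate Week 10 in Protocol 6.3.4.

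**SAP time to 300 mg on the fastest schedule** (date minus first dose date + 1), counting 20 weeks from Day 1:

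| Failed attempts at 300 mg | First dose given | First dose tolerated |
|---|---|---|
| 0 | 140 + 1 = day 141 | day 141 |
| 1 | day 141 | 141 + 14 = day 155 |
| 2 | day 141 | 141 + 28 = day 169 |
| never tolerated | event at day 141 | censored at last dose |

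Counting from Day 2, as a Table 2 footnote may be read, adds one day to every dated entry and leaves the differences unchanged.

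The 14 days per failed attempt is a typical value, not a minimum. Protocol 6.5.5 permits reductions shorter than 2 weeks, and Protocol 6.8 allows visits to vary by 2 days. After severe symptoms or in-clinic epinephrine the dose falls by two levels (Protocol 6.5.5.1 and 6.5.6), which can make the delay longer.

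**Group effect, illustration only.** The documents give no failure rate. Assumed: 500 × 2/3 = 333 AR101 children; 20% stop before 300 mg; 2% to 20% of the rest fail their first 300 mg dose; 25% to 50% of those never tolerate it; other delays come in 14-day steps averaging one step. Over 100 simulated trials per setting:
- Crude share counted as reaching 300 mg: 80.1% under the literal rule, and 79.7% down to 71.8% under the tolerated-dose rule. The difference is 80.1 − 79.7 = 0.4 to 80.1 − 71.8 = 8.3 percentage points.
- Kaplan-Meier median: day 155 under both rules in every setting.

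The crude share is a simple proportion and is not read from the Kaplan-Meier curve, where a censored child leaves the risk set instead of counting as a failure.

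**Maximum dose.** The categories 0.5, 1 and 1.5 mg are given only as Day 1 steps (Protocol Table 1), and the item sits among exposure measures, so *administered* is the more natural reading. The two meanings can differ. Under Protocol 6.3.1 a child with dose-limiting symptoms only at the 6 mg step on Day 1 returns for 3 mg on Day 2. If that child goes no further, the highest dose given is 6 mg and the highest tolerated can be 3 mg.

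**The case against.** The best defence is that the protocol itself separates reaching 300 mg from tolerating it. Protocol 6.3.5 makes the first 300 mg in-clinic visit the end of up-dosing, and the following two weeks are there to establish tolerability. On that view SAP 7.1 and the time-to-dose rule follow the protocol's milestone, and time to first administration is a proper exposure measure. This stands to the extent that such a curve is legitimate under that label. It does not explain why SAP 9.5 and 9.8.1 adopt a different milestone for the periods, or settle what *reach* means in the censoring rule.

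Much is also reported elsewhere. SAP 9.5 counts unsuccessful dose increases, SAP 9.1 shows how many entered each period, and SAP 9.8.6 shows symptoms by dose level. Adverse events are already allocated to periods by the tolerated-dose rule. All of this stands and limits the harm, but none of it corrects the curve.

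A reader might infer that the SAP counts a failed dose as the maximum dose achieved. The documents do not say so; the term is undefined, and a maximum administered dose is acceptable in an exposure section. A reader might also infer that the reported median is too early, or that a known number of children are misdated. The illustration shows the median need not move, and no failure rate is given. That failures fall mainly on AR101 is plausible but is likewise not stated.

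Finally, a tolerated-dose event would not equal escalation success. The protocol also counts as a failure a child who cannot tolerate 300 mg daily for 2 weeks by week 48, and such a child may have tolerated the first clinic dose.

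**Conclusion.** The inconsistency is real and rests on the text alone. The time-to-dose event in SAP 9.5 has no tolerance condition. The 300 mg period rules in 9.5 and 9.8.1 have one, and 7.1 agrees with neither. For an affected child the date is early by about 14 days per failed attempt on the usual 2-week schedule, and a child who never tolerates the level becomes a false event. The size at group level cannot be derived from the documents; the 0.4 to 8.3 point range depends wholly on the assumed rates.

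For maximum dose the finding is only that a term is undefined. Severity is minor to moderate: these are descriptive exposure outputs, not primary, secondary or exploratory endpoints. The 7.1 mismatch deserves the more care, because it can affect the person-time behind the up-dosing rates.

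**What to change.** 1. In SAP 9.5, define the time-to-300 mg event as the first in-clinic 300 mg dose that was tolerated and continued at home, using the rule already in the period table. Write the matching rule for 80 mg, and censor children who never meet it. If time to first administered dose is also wanted, show it separately under that name.
2. In SAP 7.1, align the end of up-dosing with 9.5 and 9.8.1 so that no interval falls between periods. Note that this analysis boundary differs from the visit label in Protocol 6.3.5.
3. Relabel *maximum dose achieved* as maximum dose administered, and add a row for maximum dose tolerated with a none-tolerated category. This row should carry no home-dosing condition: such a condition would leave initial-escalation failures without a value and the 0.5, 1 and 1.5 mg categories empty.
4. Name the recorded variable that identifies a tolerated dose. SAP 9.8.6 says dose-limiting symptoms are recorded for each site dose, and 9.5 already derives unsuccessful increases.

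The cost is SAP wording and minor programming. The tolerated 300 mg date is already derived for the period table, and no new data are needed. Reported times may look slightly less favourable. Only analysis definitions change; no dosing rule is touched.
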